2.3.3 Best Overall Response

Best response determination of complete or partial response requires confirmation: Complete or partial responses may be claimed only if the criteria for each are met at a subsequent time point of ≥ 4 weeks (28 days) later. In this circumstance, the best overall response can be interpreted as in Table 2.3.3-1. When SD is believed to be best response, it must meet the protocol specified minimum time from the date of first treatment or randomization date.

For example, if the first scheduled follow-up imaging visit is Week 6 (± 7 days) for a particular protocol, a Best Response of SD can only be made after the subject is on-study for a minimum of 6 weeks (42 days) minus 7 days, for an absolute minimum time on-study of 35 days from the reference start date (reference date is considered Day 1 on study). If the subject is not on-study for at least this amount of time, any tumor assessment indicating stable disease before this time period will have a Best Response of NE unless PD is identified.

Special note on response assessment: When nodal disease is included in the sum of target lesions and the nodes decrease to ‘normal’ size (< 10 mm), they may still have a measurement reported on scans. This measurement should be recorded even though the nodes are normal in order not to overstate progression should it be based on increase in size of the nodes. As noted earlier, this means that patients with CR may not have a total sum of ‘zero’ on the case report form (CRF).

Table 2.3.3-1: Best Overall Response (Confirmation of CR and PR Required)		
Overall Response First Time Point	Overall Response Subsequent Time Point	Best Overall Response
CR	CR	CR
CR	PR	SD, PD OR PR ^a
CR	SD	SD provided minimum criteria for SD duration met, otherwise, PD
CR	PD	SD provided minimum criteria for SD duration met, otherwise, PD
CR	NE	SD provided minimum criteria for SD duration met, otherwise, NE

Table 2.3.3-1: Best Overall Response (Confirmation of CR and PR Required)		
Overall Response First Time Point	Overall Response Subsequent Time Point	Best Overall Response
PR	CR	PR
PR	PR	PR
PR	SD	SD
PR	PD	SD provided minimum criteria for SD duration met, otherwise, PD
PR	NE	SD provided minimum criteria for SD duration met, otherwise, NE
NE	NE	NE

CR = complete response, PR = partial response, SD = stable disease, PD = progressive disease, and NE = inevaluable

^a If a CR is truly met at first time point, then any disease seen at a subsequent time point, even disease meeting PR criteria relative to baseline, makes the disease PD at that point (since disease must have reappeared after CR). Best response would depend on whether minimum duration for SD was met. However, sometimes ‘CR’ may be claimed when subsequent scans suggest small lesions were likely still present and in fact the patient had PR, not CR at the first time point. Under these circumstances, the original CR should be changed to PR and the best response is PR.

2.3.4 Confirmation Scans

Verification of Response: To be assigned a status of CR or PR, changes in tumor measurements must be confirmed by consecutive or subsequent repeat assessments that should be performed no less than 28 days after the criteria for response are first met. Subsequent documentation of a CR may provide confirmation of a previously identified CR even with an intervening NE or PR (eg, CR NE CR or CR PR CR). Subsequent documentation of a PR may provide confirmation of a previously identified PR even with an intervening NE or SD (eg, PR NE PR or PR SD PR). However, only one (1) intervening time point will be allowed between PR/CRs for confirmation.

Verification of Progression: Progression of disease should be verified in cases where progression is equivocal. If repeat scans confirm PD, then progression should be declared using the date of the initial scan. If repeat scans do not confirm PD, then the subject is considered to not have progressive disease.

REFERENCE

¹ Eisenhauer EA, Therasse P, Bogaerts J, et al. New response evaluation criteria in solid tumors: revised RECIST guideline (version 1.1). Eur J Cancer 2009; 45: 228-47.

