2 RESPONSE CRITERIA

2.1 Evaluation of Target Lesions

- **Complete Response (CR):** Disappearance of all target lesions. Any pathological lymph nodes (whether target or non-target) must have reduction in short axis to < 10 mm.
- **Partial Response (PR):** At least a 30% decrease in the sum of diameters of target lesions, taking as reference the baseline sum diameters.
- **Progressive Disease (PD):** At least a 20% increase in the sum of diameters of target lesions, taking as reference the smallest sum on study (this includes the baseline sum if that is the smallest on study). In addition to the relative increase of 20%, the sum must also demonstrate an absolute increase of at least 5 mm. (Note: the appearance of one or more new lesions is also considered progression).
- **Stable Disease (SD):** Neither sufficient shrinkage to qualify for PR nor sufficient increase to qualify for PD, taking as reference the smallest sum diameters while on study.
- **Not Evaluable (NE):** If one or more target lesions cannot be measured or adequately assessed as either fully resolved or too small to measure (due to missing or poor quality images), and the sum of diameters of the remaining measured target lesions (if any) has not increased sufficiently to meet Progressive Disease as defined above.

2.1.1 *Special Notes on the Assessment of Target Lesions*

2.1.1.1 *Lymph nodes*

Lymph nodes identified as target lesions should always have the actual short axis measurement recorded (measured in the same anatomical plane as the baseline examination), even if the nodes regress to below 10 mm on study. This means that when lymph nodes are included as target lesions, the ‘sum’ of lesions may not be zero even if complete response criteria are met, since a normal lymph node is defined as having a short axis of < 10 mm. Case report forms or other data collection methods may therefore be designed to have target nodal lesions recorded in a separate section where, in order to qualify for CR, each node must achieve a short axis < 10 mm. For PR, SD and PD, the actual short axis measurement of the nodes is to be included in the sum of target lesions.

2.1.1.2 *Target lesions that become ‘too small to measure’*

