4.1.1 Objective Response Rate

Objective Response Rate (ORR) is defined as the number of randomized subjects who achieve a best response of confirmed complete response (CR) or confirmed partial response (PR) based on BICR assessments (using RECIST v1.1 criteria) divided by the number of all randomized subjects. If the objective is for a particular population (LAG3 positive, LAG3 negative), only that population is selected. Best Overall Response (BOR) is defined as the best response, as determined by the BICR, recorded between the date of randomization and the date of objectively documented progression per RECIST v1.1 criteria or the date of subsequent therapy (including tumor-directed radiotherapy and tumor-directed surgery), whichever occurs first. For subjects without documented progression or subsequent therapy, all available response designations will contribute to the BOR determination. Confirmation of response is required at least 4 weeks after the initial response.

When the objective is specific to the investigator assessment, the above definition is altered to exchange BICR for investigator assessment in the derivation of the endpoint.

Time to Response

Time to Response (TTR) is defined as the time from randomization to the date of the first confirmed documented response (CR or PR), as assessed by the BICR. TTR will be evaluated for responders (confirmed CR or PR) only.

When the objective is specific to the investigator assessment, the above definition is altered to exchange BICR for investigator assessment in the derivation of the endpoint.

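### Appendix 5 gives incompatible results for the scan sequence CR-PR-CR: a confirmed CR under section 2.3.4, but SD with progression, or PR, under Table 2.3.3-1 and its footnote a

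*Protocol*

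**What the plan says.** Protocol 9.1.3 sends the reader to Appendix 5 for the RECIST 1.1 rules. These places bear on a PR that follows a CR:

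- **Appendix 5, 2.3.4, first paragraph.** "Subsequent documentation of a CR may provide confirmation of a previously identified CR even with an intervening NE or PR", with the example "eg, CR NE CR or CR PR CR". It adds that "only one (1) intervening time point will be allowed between PR/CRs for confirmation".
- **Appendix 5, Table 2.3.3-1, row CR then PR.** Best overall response is limited to SD, PD or PR. CR is not listed.
- **Footnote a to that table.** It has two branches. If the first CR was truly met, "any disease seen at a subsequent time point, even disease meeting PR criteria relative to baseline, makes the disease PD at that point", and best response depends on whether the minimum SD duration was met. If later scans suggest that small lesions had probably been present throughout, "Under these circumstances, the original CR should be changed to PR and the best response is PR".
- **Appendix 5, 2.3.4, second paragraph.** Equivocal progression should be verified, and a PD that repeat scans do not confirm is set aside.
- **Appendix 5, 2.1.** For CR, "Any pathological lymph nodes (whether target or non-target) must have reduction in short axis to < 10 mm". PD by size needs an increase of at least 20% and at least 5 mm over the smallest sum.

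In SAP 4.1.1, best overall response is the best one "recorded between the date of randomization and the date of objectively documented progression per RECIST v1.1 criteria", or up to subsequent therapy if that comes first. SAP 4.1.2 and 4.1.3.1 end DOR and PFS at the first documented progression or death.

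**The concern.** The confirmation paragraph treats the middle scan of CR-PR-CR as a harmless gap between two complete responses. Footnote a can treat the same scan as progression. Once progression is recorded, the best-response window closes and the later CR cannot count. The same images can therefore lead to different best responses, different PFS outcomes and a different DOR, and neither document ranks the rules.

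Appendix 5 feeds the primary endpoint (BICR ORR in LAG-3 positive participants) and the ORR, DOR and PFS analyses by BICR and by investigator. A site, a central reader and the SAP program could each follow the text and differ. Some of that difference could then appear as disagreement in the BICR-versus-investigator cross-tabulation of SAP 7.5.1. The choice can also affect which scans exist: scheduled imaging runs until BICR-confirmed progression, so a PD reading at the middle scan may mean the third scan is not obtained.

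**Working it through.** The plan states no figure on this point, so there is none to reproduce. The check applies each rule to one scan series.

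**Inputs.** Scans every 6 weeks ± 7 days to Week 48 (Protocol Tables 2-2 and 2-3). Confirmation at least 28 days later, with at most one intervening time point (Appendix 5, 2.3.4). SD needs at least 35 days from randomization (Protocol 9.1.3). About 250 participants randomized 1:1 (Protocol 10.1). The LAG-3 positive number is not in the public text, so 50 per arm (40% of 125) is an assumption.

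**Series.** CR at Week 6 (day 42), PR at Week 12 (day 84), CR at Week 18 (day 126), with no earlier response.

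**Timing.** The shortest CR-to-CR gap is (126 − 7) − (42 + 7) = 70 days and the longest is (126 + 7) − (42 − 7) = 98 days. Both exceed 28, and one scan intervenes, so 2.3.4 is satisfied. The first scan falls on days 35 to 49, so the SD minimum is met.

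| Rule applied | Best response | Responder | PFS at day 84 | DOR |
|---|---|---|---|---|
| 2.3.4 confirmation | CR | yes | no event | starts day 42, no event through day 126 |
| Footnote a, true CR | SD | no | event | not defined |
| Footnote a, CR re-designated | PR | yes | no event | starts day 42, no event through day 126 |

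**Where the verification clause acts.** If the Week 12 finding is equivocal and Week 18 does not confirm it, the PD is withdrawn and the second row drops out. What then remains is whether the category is CR (2.3.4) or not (Table 2.3.3-1). If the reappearance is unequivocal, the clause does not reach it and the second row stands against the first.

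**When ORR is untouched.** Take PR (day 42), CR (day 84), PR (day 126), CR (day 168). The shortest gap between the first two scans is (84 − 7) − (42 + 7) = 28 days, which is enough. The table row PR then CR gives best response PR, so the participant is a responder before footnote a applies. Only the CR category, PFS and DOR can then change.

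**Size where ORR does change.** One participant moves an arm's ORR by 100/n points:

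- n = 250/2 = 125: 100/125 = 0.8 points
- n = 50 (assumed LAG-3 positive per arm): 100/50 = 2.0 points

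**A nodal example.** Take a single target node with an assumed 20 mm baseline, then 9, 11 and 9 mm.

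- At 9 mm it is below the 10 mm limit, so CR is possible.
- At 11 mm the fall from baseline is (20 − 11)/20 = 45%, so PR.
- From 9 to 11 mm the change is 2/9 = +22% but only +2 mm. The 20% element is met and the 5 mm element is not, so PD by size fails.

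**The case against.** The strongest reply is that the rules can be read together. Table 2.3.3-1 covers two time points, and 2.3.4 extends it to three, as it does for CR NE CR and PR SD PR. The verification clause sits in the same section and withdraws a PD that the next scan does not confirm. The BICR charter, where Protocol 5.1.4 and SAP 2.5 place the reading procedures, may also rank the rules.

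Part of this stands. The verification clause does resolve the progression question for equivocal findings. The charter is not among the documents and could settle central reading. The extension argument is weaker: NE and SD are not progression, so the window stays open in those examples, whereas footnote a can make the middle scan of CR-PR-CR progression. Investigator-assessed ORR, DOR and PFS are also endpoints, and sites work from Appendix 5.

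A reader might infer that every participant with CR-PR-CR switches between non-responder and complete responder. The documents do not support that. The re-designation branch and any earlier confirmed PR both leave a responder. Nor does the 9, 11, 9 mm node show a clear progression: it misses the size criterion, and a special note in Appendix 5, 2.3.3 keeps nodal measurements so that progression is not overstated. It shows a case the text leaves unclear.

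**Conclusion.** The inconsistency is real and lies in current text. For CR-PR-CR, section 2.3.4 gives a confirmed CR, which Table 2.3.3-1 does not allow, and footnote a gives either PD at the PR scan or best response PR. The conflict over PD persists where the reappearance is unequivocal.

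The effect on ORR is narrow. It needs footnote a's progression branch and no earlier confirmed response, for example a CR at the first scan. Each such participant is worth 0.8 points at 125 per arm, or 2.0 points if 50 per arm are LAG-3 positive (an assumption). In other cases only the CR category, PFS and DOR can be affected.

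The sequence should be uncommon because it requires a CR first, but the documents give no frequency. They therefore do not support a claim that the primary comparison is materially biased. The case for acting is that the trial is open-label and the rule should not be chosen case by case with treatment known.

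**What to change.** In Appendix 5, 2.3.4, remove the intervening PR from the CR confirmation sentence and CR PR CR from its example, keeping CR NE CR. Then state one order of rules for a PR after a CR:

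1. If the reappearance is equivocal, apply the verification-of-progression clause first.
2. If later scans indicate that small lesions were probably still present at the first CR, re-designate that CR as PR, with best response PR.
3. If disease has unequivocally reappeared after a true CR, record PD at that scan.

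Add how to score nodes that fluctuate around 10 mm without meeting the combined 20% and 5 mm criterion. Put the same rule in the BICR charter and in the SAP derivations of best response, DOR and PFS.

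The cost is a short edit to Appendix 5 with matching charter text and programming. The downside is slightly fewer confirmed CRs, because some become PR.

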APPENDIX 6 ECOG STATUS SCALE

PERFORMANCE STATUS CRITERIA: ECOG Score	
ECOG (Zubrod)	
Score	Description
0	Fully active; able to carry on all pre-disease performance without restriction
1	Restricted in physically strenuous activity but ambulatory and able to carry out work of alight or sedentary nature, e.g., light house work, office work.
2	Ambulatory and capable of all self care but unable to carry out any work activities; up and about more than 50% of waking hours.
3	Capable of only limited self care; confined to bed or chair more than 50% of waking hours.
4	Completely disabled; cannot carry on any self care; totally confined to bed or chair.

APPENDIX 7 COUNTRY SPECIFIC REQUIREMENTS

Argentina, Czech Republic, France, Germany, Italy, Spain, Peru and Any Other Countries Where Exclusion of HIV Positive Participants Is Locally Mandated

	Country-specific language
Section 2 Flow Chart/Time and Events Schedule, Table 2-1: Screening Assessments- Laboratory Tests	Add “HIV” to the list of laboratory tests
Section 6.2 Exclusion Criteria, Exclusion criterion 3j	“Known history of testing positive for human immunodeficiency virus (HIV) or known acquired immunodeficiency syndrome (AIDS)”to be replaced with “Positive test for HIV”.

APPENDIX 8 MANAGEMENT ALGORITHMS

These general guidelines constitute guidance to the Investigator and may be supplemented by discussions with the Medical Monitor representing the Sponsor. The guidance applies to all immuno-oncology agents and regimens.

A general principle is that differential diagnoses should be diligently evaluated according to standard medical practice. Non-inflammatory etiologies should be considered and appropriately treated.

[figure not shown]
Corticosteroids are a primary therapy for immuno-oncology drug-related adverse events. The oral equivalent of the recommended IV doses may be considered for ambulatory patients with low-grade toxicity. The lower bioavailability of oral corticosteroids should be taken into account when switching to the equivalent dose of oral corticosteroids.

Consultation with a medical or surgical specialist, especially prior to an invasive diagnostic or therapeutic procedure, is recommended.

The frequency and severity of the related adverse events covered by these algorithms will depend on the immuno-oncology agent or regimen being used.

GI Adverse Event Management Algorithm

Rule out non-inflammatory causes. If non-inflammatory cause is identified, treat accordingly and continue I-O therapy. Opiates/narcotics may mask symptoms of perforation. Infliximab should not be used in cases of perforation or sepsis.

[figure not shown]

Patients on IV steroids may be switched to an equivalent dose of oral corticosteroids (e.g. prednisone) at start of tapering or earlier, once sustained clinical improvement is observed. Lower bioavailability of oral corticosteroids should be taken into account when switching to the equivalent dose of oral corticosteroids.

27-Jun-2018

Renal Adverse Event Management Algorithm

Rule out non-inflammatory causes. If non-inflammatory cause, treat accordingly and continue I-O therapy.

[figure not shown]

Patients on IV steroids may be switched to an equivalent dose of oral corticosteroids (e.g. prednisone) at start of tapering or earlier, once sustained clinical improvement is observed. Lower bioavailability of oral corticosteroids should be taken into account when switching to the equivalent dose of oral corticosteroids.

27-Jun-2018

Pulmonary Adverse Event Management Algorithm

Rule out non-inflammatory causes. If non-inflammatory cause, treat accordingly and continue I-O therapy. Evaluate with imaging and pulmonary consultation.

[figure not shown]

Patients on IV steroids may be switched to an equivalent dose of oral corticosteroids (e.g. prednisone) at start of tapering or earlier, once sustained clinical improvement is observed. Lower bioavailability of oral corticosteroids should be taken into account when switching to the equivalent dose of oral corticosteroids

27-Jun-2018

Hepatic Adverse Event Management Algorithm

Rule out non-inflammatory causes. If non-inflammatory cause, treat accordingly and continue I-O therapy. Consider imaging for obstruction.

[figure not shown]
Patients on IV steroids may be switched to an equivalent dose of oral corticosteroids (e.g. prednisone) at start of tapering or earlier, once sustained clinical improvement is observed. Lower bioavailability of oral corticosteroids should be taken into account when switching to the equivalent dose of oral corticosteroids.

*The recommended starting dose for grade 4 hepatitis is 2 mg/kg/day methylprednisolone IV.

27-Jun-2018

Endocrinopathy Adverse Event Management Algorithm

Rule out non-inflammatory causes. If non-inflammatory cause, treat accordingly and continue I-O therapy. Consider visual field testing, endocrinology consultation, and imaging.

[figure not shown]

Patients on IV steroids may be switched to an equivalent dose of oral corticosteroids (e.g. prednisone) at start of tapering or earlier, once sustained clinical improvement is observed. Lower bioavailability of oral corticosteroids should be taken into account when switching to the equivalent dose of oral corticosteroids.

27-Jun-2018

Neurological Adverse Event Management Algorithm

Rule out non-inflammatory causes. If non-inflammatory cause, treat accordingly and continue I-O therapy.

[figure not shown]

Patients on IV steroids may be switched to an equivalent dose of oral corticosteroids (e.g. prednisone) at start of tapering or earlier, once sustained clinical improvement is observed. Lower bioavailability of oral corticosteroids should be taken into account when switching to the equivalent dose of oral corticosteroids.

27-Jun-2018

Skin Adverse Event Management Algorithm

Rule out non-inflammatory causes. If non-inflammatory cause, treat accordingly and continue I-O therapy.

Patients on IV steroids may be switched to an equivalent dose of oral corticosteroids (e.g. prednisone) at start of tapering or earlier, once sustained clinical improvement is observed. Lower bioavailability of oral corticosteroids should be taken into account when switching to the equivalent dose of oral corticosteroids.

[figure not shown]
*Refer to NCI CTCAE v4 for term-specific grading criteria.

**If SJS/TEN is suspected, withhold I-O therapy and refer patient for specialized care for assessment and treatment. If SJS or TEN is diagnosed, permanently discontinue I-O therapy.

27-Jun-2018

Myocarditis Adverse Event Management Algorithm

Rule out non-inflammatory causes. If non-inflammatory cause, treat accordingly and continue I-O therapy.

Patients on IV steroids may be switched to an equivalent dose of oral corticosteroids (eg, prednisone) at start of tapering or earlier, once sustained clinical improvement is observed. Lower bioavailability of oral corticosteroids should be taken into account when switching to the equivalent dose of oral corticosteroids.

Prophylactic antibiotics should be considered in the setting of ongoing immunosuppression.

ATG = anti-thymocyte globulin; BNP = B-type natriuretic peptide; ECG = electrocardiogram; I-O = immuno-oncology; IV = intravenous; MRI = magnetic resonance imaging

APPENDIX 9 REVISED PROTOCOL SUMMARY OF CHANGE HISTORY

Overall Rationale for the Revised Protocol 02, 16-Nov-2018

To [REDACTED] include updates to reflect current data and protocol standards, and make administrative corrections.

Summary of key changes for Revised Protocol 02		
Section Number & Title	Description of Change	Brief Rationale
Synopsis	Added text reflecting addition of Data Monitoring Committee.	BMS development decision
Table 2-1 Screening Assessments - All Participants (CA224060)	Added language providing for the optional collection of tumor tissue older than 3 month	Revision to Translational Medicine scope of investigation
3.3 Benefit/Risk Assessment	Revised text and added text reflecting addition of updated safety data and Data Monitoring Committee.	Reflects updated data
5.1.1 Screening Phase	Removed language requiring an associated pathology report to accompany FFPE tissue block or unstained tumor tissue section for biomarker evaluation prior to randomization; pathology report is optional. Added language providing for the optional collection of tumor tissue older than 3 months	Administrative correction Revision to Translational Medicine scope of investigation
5.1.5 Data Monitoring Committee	Added section defining use of Data Monitoring Committee.	BMS development decision
6.1 Inclusion Criteria	Removed language requiring an associated pathology report to accompany FFPE tissue block or	Administrative correction

Summary of key changes for Revised Protocol 02		
Section Number & Title	Description of Change	Brief Rationale
	unstained tumor tissue section for biomarker evaluation prior to randomization; pathology report is optional.	
6.2 Exclusion Criteria	Revised language excluding participants who received live/attenuated vaccines within 30 days of first treatment Removed exclusion of recombinant human erythropoietin within 3 weeks of first study drug administration	Reflects new required content Administrative correction
7.2 Method of Treatment Assignment	Added text regarding treatment access rules	Procedural clarification
7.3.9 Management Algorithms for Immuno-Oncology Agents	Added “Myocarditis” to list of available algorithms for guidance on management and treatment of myocarditis	To meet current standards
7.6.1 Prohibited and/or Restricted Treatments	Added prohibition of any live/attenuated vaccine during treatment up to 100 days post treatment	To meet current standards
9.2.1 Time Period and Frequency for Collecting AE and SAE Information	Removal of prescreening consent option	Administrative correction

Summary of key changes for Revised Protocol 02		
Section Number & Title	Description of Change	Brief Rationale
10.3.9 Interim Analyses	Revised text to incorporate analyses for DMC evaluation of risk/benefit	BMS development decision
Appendix 3	Updated definitions and procedures for recording, evaluating, follow-up and reporting AEs and SAEs	To meet current standards
Appendix 8	Added “Myocarditis” to list of available algorithms for guidance on management and treatment of myocarditis	To meet current standards
All	Minor formatting and typographical corrections	Minor, therefore have not been summarized

Overall Rationale for the Revised Protocol 01, 29-Jun-2018

The primary purpose for this revision was to update Appendix 4, WOCBP to current standards, and to modify the PD-L1 stratification levels.

Summary of key changes for Revised Protocol 01		
Section Number & Title	Description of Change	Brief Rationale
All	Modified PD-L1 stratification levels for statistical analyses	Due to a change in methodology and evolving understanding of the relevant cutoffs for the gastric population

Summary of key changes for Revised Protocol 01		
Section Number & Title	Description of Change	Brief Rationale
Section 6.2 Exclusion Criteria	Additional exclusion criterion added	
Section 8.1 Discontinuation from Study Treatment	Modified text to include consideration by the investigator of abnormal liver tests for participant discontinuation, and revision of procedures to follow in case of pregnancy	To meet current standards
Section 9.2.1 Time Period and Frequency for Collecting AE and SAE Information	Modified text regarding collection of AE and SAE information	To meet current standards
Appendix 4	Updated appendix for WOCBP	To meet current standards
All	Updated CTCAE to version 5	To meet current standards
All	Minor formatting and typographical corrections	Minor, therefore have not been summarized
